## 17 Changes from the protocol specified statistical analysis

After the study was submitted to the MHRA and ethics committee the following changes were made to the analyses:

- Various updates to scheduled timepoints have been made as document in file note ward 2.

## **19 ATTACHMENTS**

### **19.1 Table of contents for data display specifications**

For overall page layout refer to Appendix C: Sample page .

The numbering in the tables below will take precedence over the numbering in the shells.

The following tables and figures will be produced (templates provided in Sections 19.2.1 and 19.2.2):

Table	Description	Population	Source Listing	Template (Shells below)
10.1	Summary of subject disposition	Safety	16.2.1.2 16.2.1.3 16.2.3.1	T_SD1
14.1	DEMOGRAPHIC DATA			
14.1	Summary of demographic characteristics	Safety	16.2.4.1	T_DM1
14.2	PHARMACOKINETIC AND PHARMACODYNAMIC DATA			
14.2.1.1	Summary of ASN51 plasma pharmacokinetic concentration-time data [units]	PK analysis	16.2.6.1.1	T_PK1
14.2.1.2	Summary of derived ASN51 plasma pharmacokinetic parameters	PK analysis	16.2.6.1.2 16.2.6.1.3	T_PK3
14.2.1.3	Summary of log-transformed derived ASN51 plasma pharmacokinetic parameters	PK analysis	16.2.6.1.2 16.2.6.1.3	T_PK4
14.2.2.1	Summary of plasma PBMC data (% above baseline)	PD analysis	16.2.6.2	T_VS1
14.2.2.2	Summary of analysis of time-matched change from baseline plasma PBMC data using analysis of variance (Day 1 vs Day 14 and Day 11 vs Day 14)	PD analysis	16.2.6.2	T_ANOVA1
14.2.2.3	Summary of ANCOVA analysis of PBMC and PK concentration to compare intercepts and slopes between Day 1 and Day 14	PD analysis	16.2.6.2	T_REGR
14.3	SAFETY DATA			
14.3.1.1	Overall summary of treatment-emergent adverse events	Safety	16.2.7.1	T_AE2
14.3.1.2	Summary of treatment-emergent adverse events	Safety	16.2.7.1	T_AE1
14.3.1.3	Summary of drug-related treatment-emergent adverse events	Safety	16.2.7.1	T_AE1
14.3.2.1	Listing of fatal adverse events	Safety	16.2.7.1	L_AE1_PG
14.3.2.2	Listing of non-fatal serious adverse events	Safety	16.2.7.1	L_AE1_PG
14.3.2.3	Listing of other significant adverse events	Safety	16.2.7.1	L_AE1_PG
14.3.3	Narratives of deaths, other serious and significant adverse events	Safety	-	-
14.3.4.1	Summary of laboratory values outside the reference range by treatment and planned relative time	Safety	16.2.8.1 16.2.8.2 16.2.8.3	T_LB1

Table	Description	Population	Source Listing	Template (Shells below)
14.3.4.2	Summary of laboratory values outside the reference range by treatment	Safety	16.2.8.1 16.2.8.2 16.2.8.3	T_LB3
14.3.5.1	Summary of chemistry laboratory values	Safety	16.4	T_LB2
14.3.5.2	Summary of haematology laboratory values	Safety	16.4	T_LB2
14.3.5.3	Summary of coagulation laboratory values	Safety	16.4	T_LB2
14.3.5.4	Summary of urinalysis results	Safety	16.4	T_UR1
14.3.6.1	Summary of vital signs	Safety	16.4	T_VS1
14.3.6.2	Summary of vital signs outside the normal range by treatment, planned relative time and parameter	Safety	16.2.9.1	T_VS2
14.3.6.3	Summary of vital signs outside the normal range by treatment and parameter (excluding baseline time point)	Safety	16.2.9.1	T_VS3
14.3.7.1	Summary of ECG values	Safety	16.4	T_EG2
14.3.7.2	Summary of QTcF and PR interval values outside the normal range by treatment, planned relative time and category	Safety	16.2.9.3	T_EG3
14.3.7.3	Summary of QTcF and PR interval values outside the normal range by treatment and category	Safety	16.2.9.3	T_EG4

Figure	Description	Population	Source Listing	Template (Shells below)
14.2	PHARMACOKINETIC AND PHARMACODYNAMIC DATA			
14.2.1	Individual ASN51 plasma concentration-time plots (linear and semi-log)	PK analysis	16.2.6.1.1	F_PK1
14.2.2	Mean (+/- SD) ASN51 plasma concentration-time plots (linear and semi-log)	PK analysis	16.2.6.1.1	F_PK2
14.2.3	Mean ASN51 plasma concentration-time plots (linear and semi-log)	PK analysis	16.2.6.1.1	F_PK2
14.2.4	Individual ASN51 plasma pre-dose concentration versus day	PK analysis	16.2.6.1.1	F_PK5
14.2.5	Mean (+/- SD) ASN51 plasma pre-dose concentration versus day	PK analysis	16.2.6.1.1	F_PK6

Figure	Description	Population	Source Listing	Template (Shells below)
14.3	SAFETY DATA			
14.3.1	Individual systolic blood pressure-time plots	Safety	16.4	F SAF1
14.3.2	Individual diastolic blood pressure-time plots	Safety	16.4	F SAF1
14.3.3	Individual heart rate-time plots	Safety	16.4	F SAF1
14.3.4	Individual QTcF-time plots	Safety	16.4	F SAF1

The following abbreviated listings will be produced (templates provided in Section 19.2.3):

Listing	Description	Template (Shells below)
16.2.1	Study dates & disposition of subjects	
16.2.1.1	Listing of study dates	L SD1 PG
16.2.1.2	Listing of reasons for withdrawal	L SD2 PG
16.2.1.3	Listing of subjects screened but not enrolled	L SD3 PG
16.2.2	Protocol deviations	
16.2.2.1	Listing of subjects with inclusion/exclusion criteria deviations	L DV1 PG
16.2.2.2	Listing of subjects with time deviations	L TD1 PG
16.2.2.3	Listing of subjects with other protocol deviations	L DV2 PG
16.2.3	Analysis sets, including subjects excluded from analysis	
16.2.3.1	Listing of analysis populations	L AN1 PG
16.2.4	Demographic data & concomitant medication	
16.2.4.1	Listing of demographic characteristics	L DM1 PG
16.2.4.2	Listing of concomitant medications	L CM1 PG
16.2.4.3	Listing of medical history	L MH1 X
16.2.5	Study drug administration	
16.2.5.1	Listing of exposure data	L EX1 PG
16.2.6	Pharmacokinetic and pharmacodynamic data	
16.2.6.1.1	Listing of ASN51 plasma pharmacokinetic concentration-time data	L PK1 PG

Listing	Description	Template (Shells below)
16.2.6.1.2	Listing of derived ASN51 plasma pharmacokinetic parameters	L PK4 PG
16.2.6.1.3	Listing of derived ASN51 Ctrough (ng/mL) pharmacokinetic parameter	L PK4 PG
16.2.6.1.4	Individual ASN51 plasma concentration-time plots for estimation of $\lambda_z$ , with regression line	F PK10
16.2.6.2	Listing of plasma PBMC data	L PBMC PG
16.2.7	Adverse events	
16.2.7.1	Listing of all adverse events	L AE1 PG
16.2.7.2	Listing of serious adverse events	L AE1 PG
16.2.7.3	Listing of adverse events leading to withdrawal from study	L AE1 PG
16.2.8	Laboratory values	
16.2.8.1	Listing of clinical chemistry data outside the normal range	L LB1 PG
16.2.8.2	Listing of haematology data outside the normal range	L LB1 PG
16.2.8.3	Listing of coagulation data outside the normal range	L LB1 PG
16.2.9	Vital signs, ECG variables, physical and neurological findings and C-SSRS	
16.2.9.1	Listing of vital signs outside the normal range	L VS1 PG
16.2.9.2	Listing of clinically significant vital signs	L VS2 PG
16.2.9.3	Listing of QTcF and PR interval values outside the normal range	L EG1 PG
16.2.9.4	Listing of abnormal ECG findings	L EG2 PG
16.2.9.5	Listing of abnormal physical examination findings	L PE1 PG
16.2.9.6	Listing of abnormal neurological examination findings	L NEURO PG
16.2.9.7	Listing of positive Columbia-Suicide Severity Rating Scale data	L CSS PG

\* ICH does not require full listings of lab data so only subjects with out-of-range values will be listed.

Complete listings of all data collected in this study will also be produced.

## 19.2 Data Display Specifications

Footnote “Note: Subjects received ASN51 in the fed state on Day 11 only” will be added to any outputs with Day 11

### 19.2.1 Table Outlines

#### Template T\_SD1

Table 10.1 Summary of subject disposition

Characteristics	Status	Reason for Withdrawal	Treatment 1 (N=xx) n (%)	Treatment 2 (N=xx) n (%)	All Subjects n (%)
Screened population	Total				xx
	Included				xx
	Excluded	Not satisfying inclusion/exclusion criteria			xx
		Declined to participate			xx
Safety population	Other				xx
	Included		xx	xx	xx
	Completed		xx (xx)	xx (xx)	xx (xx)
	Withdrawn		xx (xx)	xx (xx)	xx (xx)
	Death		xx (xx)	xx (xx)	xx (xx)
	Adverse Events		xx (xx)	xx (xx)	xx (xx)
	Withdrawal by subject		xx (xx)	xx (xx)	xx (xx)
	Study terminated by Sponsor		xx (xx)	xx (xx)	xx (xx)
	Lost to follow-up		xx (xx)	xx (xx)	xx (xx)
	Other		xx (xx)	xx (xx)	xx (xx)
Alternative 1 (if applicable)	Included				
Alternative 2 (if applicable)	Included				

Source: Listing 16.2.xx

Note: Subjects received ASN51 in the fed state on Day 11 only

Programming notes: *Continued with all treatment groups*

**Template T\_DM1**

Table 14.1 Summary of demographic characteristics

Variable	Statistics	Treatment 1 (N=xx)	Treatment 2 (N=xx)	All Subjects (N=xx)
Age (y)	n			
	Mean			
	SD			
	Median			
	Min			
	Max			
Sex (%)	Female			
	Male			
Race (%)	American Indian or Alaskan			
	Native			
	Asian			
	Black			
	Native Hawaiian or other			
	Pacific Islander			
	White			
	Other			
Ethnicity (%)	Hispanic or Latino			
	Not Hispanic or Latino			
Height (cm)	n			
	Mean			
	SD			
	Median			
	Min			
	Max			
Weight (kg)	n			
	Mean			
	SD			
	Median			
	Min			

Variable	Statistics	Treatment 1	Treatment 2	All Subjects (N=xx)
		(N=xx)	(N=xx)	
BMI (kg/m2)	Max			
	n			
	Mean			
	SD			
	Median			
	Min			
	Max			
Smoking	Never			
History (%)	Former			
	Current			
Cigarettes* (daily)	n			
	Mean			
	SD			
	Median			
	Min			
	Max			
Alcohol* (units/week)	n			
	Mean			
	SD			
	Median			
	Min			
	Max			

Source: Listing 16.2.xx

\*includes only those subjects who smoke/drink alcohol

**Template T\_PK1**

Table 14..2.xx Summary of ASN51 plasma pharmacokinetic concentration-time data [units]

Treatment	Planned Relative Time	n	No. Imputed	Mean	95% CI (Lower,Upper)	SD	%CVb	Median	Min	Max
Treatment 1 (N=xx)	Pre-dose	x	x	xxxx.x	(xxxx.x,xxxx.x)		xx.x	xxxx.x	xxxx	xxxx
	30 min	x	x	xxxx.x	(xxxx.x,xxxx.x)	xx.xx	xx.x	xxxx.x	xxxx	xxxx
	1 h	x	x	xxxx.x	(xxxx.x,xxxx.x)	xx.xx	xx.x	xxxx.x	xxxx	xxxx
Treatment 2 (N=xx)	Pre-dose	x	x	xxxx.x	(xxxx.x,xxxx.x)	xx.xx	xx.x	xxxx.x	xxxx	xxxx
	30 min	x	x	xxxx.x	(xxxx.x,xxxx.x)	xx.xx	xx.x	xxxx.x	xxxx	xxxx
	1 h	x	x	xxxx.x	(xxxx.x,xxxx.x)	xx.xx	xx.x	xxxx.x	xxxx	xxxx

Source: Listing 16.2.xx

Programming notes: *Continued with all dose levels and timepoints*

*Column "No. Imputed" is not required for summary of PBMC data*

**Template T\_PK3**

Table 14..2.xx Summary of derived ASN51 plasma pharmacokinetic parameters

Parameter	Treatment	Study Day	n	Mean	95% CI (Lower,Upper)	SD	%CVb	Median	Min	Max
AUC t (units)	Treatment 1 (N=xx)		xx	xxxx.xx	(xxxx.xx,xxxx.xx)	xx.xxx	xx.x	xxxx.xx	xxxx.x	xxxx.x
	Treatment 2 (N=xx)		xx	xxxx.xx	(xxxx.xx,xxxx.xx)	xx.xxx	xx.x	xxxx.xx	xxxx.x	xxxx.x
C max (units)	Treatment 1 (N=xx)		xx	xxxx.xx	(xxxx.xx,xxxx.xx)	xx.xxx	xx.x	xxxx.xx	xxxx.x	xxxx.x
	Treatment 2 (N=xx)		xx	xxxx.xx	(xxxx.xx,xxxx.xx)	xx.xxx	xx.x	xxxx.xx	xxxx.x	xxxx.x

Source: Listing 16.2.xx

Rac (AUC) = Rac (AUCtau) Day 14 / Rac(AUCtau) Day 1

Rac (Cmax) = Rac (Cmax) Day 14/Rac(Cmax) Day 1

Programming notes: *Continued with all dose levels, timepoints and parameters*

**Template T\_PK4**

Table 14..2.xx Summary of log-transformed derived ASN51 plasma pharmacokinetic parameters {by group}

Parameter	Treatment	Study Day	n	Geom Mean	95% CI (Lower,Upper)	SD (logs)	%CVb
AUC last (units)	Treatment 1 (N=xx)	x	x	xxxx.xx	(xxxx.xx,xxxx.xx)	xx.xxx	xx.xx
	Treatment 2 (N=xx)	x	x	xxxx.xx	(xxxx.xx,xxxx.xx)	xx.xxx	xx.xx
C max (units)	Treatment 1 (N=xx)	x	x	xxxx.xx	(xxxx.xx,xxxx.xx)	xx.xxx	xx.xx
	Treatment 2 (N=xx)	x	x	xxxx.xx	(xxxx.xx,xxxx.xx)	xx.xxx	xx.xx

Source: Listing 16.2.xx

*Programming notes: Continued with all dose levels, timepoints and parameters*

**Template T\_ANOVA1**

Table 14.2.xx Summary of analysis of time-matched change from baseline plasma PBMC data using analysis of variance -Day 1 vs Day 14 and Day 11 vs Day 14 (% above baseline)

Treatment	RelativeTime	LS Means			Day 1 vs Day 14			Day 11 vs Day 14		
		Planned		Mean Ratio	SE	90% CI	Geometric		Mean Ratio	SE
		Day 1	Day 11				Day 1	Day 14		
Treatment 1 (N=xx)	Pre-dose	NA	xxxx	NA	NA	NA	x.xx	x.xx	x.xx	x.xx
	8 h	xxxxx	xxxx	x.xx	x.xx	(x.xx, x.xx)	x.xx	x.xx	(x.xx, x.xx)	
	12 h	xxxxx	xxxx	x.xx	x.xx	(x.xx, x.xx)	x.xx	x.xx	(x.xx, x.xx)	
Treatment 2 (N=xx)	Pre-dose	NA	xxxx	NA	NA	NA	x.xx	x.xx	x.xx	x.xx
	8 h	xxxxx	xxxx	x.xx	x.xx	(x.xx, x.xx)	x.xx	x.xx	(x.xx, x.xx)	
	12 h	xxxxx	xxxx	x.xx	x.xx	(x.xx, x.xx)	x.xx	x.xx	(x.xx, x.xx)	

Source: Listing 16.2.xx

NA = not applicable

Template T\_REGR

Table 14.2.xx Summary of ANCOVA analysis of PBMC and PK concentration to compare intercepts and slopes between Day 1 and Day 14

Treatment	Parameter	Estimate	SE	95% CI	P-Value
Treatment 1 (N=xx)	Intercept	xx.x	xx.xx	x.xxx	x.XXX
	PK Concentration	xx.x	xx.xx	x.xxx	x.XXX
	Day 1	xx.x	xx.xx	x.xxx	x.XXX
	Day 14	xx.x	xx.xx	x.xxx	x.XXX
	PK Concentration*Day 1	xx.x	xx.xx	x.xxx	x.XXX
	PK Concentration*Day 14	xx.x	xx.xx	x.xxx	x.XXX
Treatment 2 (N=xx)	Intercept	xx.x	xx.xx	x.xxx	x.XXX
	PK Concentration	xx.x	xx.xx	x.xxx	x.XXX
	Day 1	xx.x	xx.xx	x.xxx	x.XXX
	Day 14	xx.x	xx.xx	x.xxx	x.XXX
	PK Concentration*Day 1	xx.x	xx.xx	x.xxx	x.XXX
	PK Concentration*Day 14	xx.x	xx.xx	x.xxx	x.XXX

Source: Listing 16.2.xx

Programming notes: *Include timepoints: 8 h, 12h and 24 h*

**Template T\_AE2**

Table 14.3.3.xx Overall summary of treatment-emergent adverse events

Number of Subjects with	Treatment 1 (N=xx)		Treatment 1 (N=xx)		All Subjects (N=xx)	
	n	(%)	n	(%)	n	(%)
Any TEAE	x (xx.x)	[xx]	x (xx.x)	[xx]	x (xx.x)	[xx]
Any serious TEAE	x (xx.x)	[xx]	x (xx.x)	[xx]	x (xx.x)	[xx]
Any TEAE leading to withdrawal	x (xx.x)	[xx]	x (xx.x)	[xx]	x (xx.x)	[xx]
Any drug-related TEAE	x (xx.x)	[xx]	x (xx.x)	[xx]	x (xx.x)	[xx]
Any TEAE with mild as worst severity	x (xx.x)		x (xx.x)		x (xx.x)	
Any TEAE with moderate as worst severity						
Any TEAE with severe as worst severity						

Source: Listing 16.2.xx

n = number of subjects

[ ] = number of TEAEs

*Programming notes:      Continued with all treatment groups*

**Template T\_AE1**

Table 14.3.3.xx Summary of treatment-emergent adverse events

System Organ Class*	Preferred Term	Treatment 1 (N=xx) n (%)	Treatment 2 (N=xx) n (%)	All Subjects (N=xx) n (%)
Number of subjects with TEAEs		x (xx.x)	x (xx.x)	
Gastrointestinal disorders	Total number of subjects	x (xx.x)	x (xx.x)	
	Abdominal discomfort	x (xx.x) [xx]	x (xx.x) [xx]	
	Abdominal pain	x (xx.x) [xx]	x (xx.x) [xx]	
Nervous system disorders	Total number of subjects			
	Dizziness	-	-	
	Headache	-	-	
-	-	-	-	

Source: Listing 16.2.xx

n = number of subjects (subjects with >1 TEAE are counted only once per system organ class and preferred term)

[ ] = number of TEAEs

\*Coded using MedDRA version xx.x

*Programming notes: Continued with all treatment groups*

*SOCs and PTs are sorted in decreasing order of frequency*

*Presented for all applicable MedDRA system organ classes and terms.*

### Template T\_LB1

Table 14.3.4.xx Summary of laboratory values outside the reference range by treatment and planned relative time

Laboratory Test (units)	Treatment	Planned Relative Time	n	H	L
	Treatment 1 (N=xx)				

Source: Listing 16.2.xx

H = Above reference interval, L = Below reference interval

*Programming notes: Continued with all tests, treatment groups and time points. The summary is based on the reference ranges (most common ranges used)*

### Template T\_LB3

Table 14.3.4.xx Summary of laboratory values outside the reference range by treatment

Laboratory Test (units)	Treatment	m	H	L	Overall*
	Treatment 1 (N=xx)				

Source: Listing 16.2.xx

H = Above reference interval, L = Below reference interval

Subjects only counted once per treatment per category

\*Subjects only counted once per treatment

*m = total number of results for that parameter*

*Programming notes: Continued with all tests, treatment groups and time points. The summary is based on the reference ranges (most common ranges used)*

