13. Full physical and neurological examinations will be done at screening and at the follow-up visit. Brief (symptom-directed) physical examinations will be done at all other timepoints.
14. FSH tests in post-menopausal women (screening only).
15. Weight only at screening visit 2 (MRI; PET subjects only).
16. Vital signs consist of seated systolic and diastolic blood pressure, pulse rate, tympanic temperature, and respiratory rate. Vital signs will be done at the following timepoints.
 - *PBMC-only subjects*: screening; Day -1; predose and at 2, 4, 8, and 12 h postdose on Day 1; before dosing on Days 2–13; before, and at 2, 4, 8, and 12 h after dosing on Day 14; at 24 h (Day 15), 48 h (Day 16), 72 h (Day 17), 96 h (Day 18), 120 h (Day 19), and 144 h (Day 20) after the last dose of ASN51; and at follow-up
 - *PET subjects* will have the same timepoints as PBMC-only subjects, plus additional assessments at: imaging session 1 (baseline) and imaging session 3 (if held on Day 22 or Day 23)TriPLICATE measurements (obtained \geq 5 min apart) will be made at screening. Single measurements will be made at all other timepoints. Measurements should begin with subjects in a seated position, after resting for at least 5 min. Additional unscheduled assessments may be done at the discretion of the investigator. Morning vital signs should always be taken before study drug administration.
17. During the period of residence, ECGs will be recorded at the following timepoints.
 - *PBMC-only subjects*: screening; Day -1; predose and at 2, 4, 8, and 12 h postdose on Day 1; before dosing on Days 2–13; before, and at 2, 4, 8, and 12 h after dosing on Day 14; at 24 h (Day 15), 48 h (Day 16), 72 h (Day 17), 96 h (Day 18), 120 h (Day 19), and 144 h (Day 20) after the last dose of ASN51; and at follow-up
 - *PET subjects* will have the same timepoints as PBMC-only subjects, plus additional assessments at: imaging session 1 (baseline) and imaging session 3 (if held on Day 22 or Day 23)TriPLICATE recordings (obtained \geq 5 min apart) will be made at screening. Single recordings will be done at all other time points. Recordings should be made with subjects in a supine position, after resting for 5 min.

18. Laboratory safety tests consist of haematology, clinical chemistry, coagulation, and urinalysis. Samples are to be taken at screening, Day -1, before dosing on Days 8 and 14, on Day 20, and at follow-up. Samples for clinical chemistry only are to be taken at Imaging session 1.

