**Template T\_VS3**

Table 14.3.6.xx Summary of Summary of vital signs outside the normal range by treatment and parameter (excluding baseline time point)

Treatment	Systolic Blood Pressure (mmHg)		Diastolic Blood Pressure (mmHg)		Heart Rate (beats/min)		Temperature (C)		etc	Overall*	
	n	(%)	n	(%)	n	(%)	n	(%)		n	(%)
Treatment 1 (N=xx)											

Source: Listing 16.2.xx

Subjects only counted once per treatment per parameter

\*Subjects only counted once per treatment

*Programming notes: Continued with all treatments and parameters. n = total number of results for that parameter. Only include post-treatment time points*

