**Template T\_EG4**

Table 14.3.7.xx Summary of QTcF and PR interval values outside the normal range by treatment and category (excluding baseline time point)

Treatment	QTcF (msec)				PR int. (msec)				Overall*	
	451 – 480		481 – 500		> 500		>30-60			
	n	(%)	n	(%)	n	(%)	n	(%)		
Treatment 1 (N=xx)										

Source: Listing 16.2.xx

Subjects only counted once per treatment per category

[figure not shown]
\*Subjects only counted once per treatment

Programming notes: *Continued with all treatments and time points. n = total number of results for that parameter. Only include post-treatment time points*

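### The pooled laboratory out-of-range table (T_LB3, Table 14.3.4.2) takes in pre-dose results, unlike its vital-sign and ECG counterparts

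*SAP*

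**What the plan says.** SAP section 19.1 lists Table 14.3.4.2 as "Summary of laboratory values outside the reference range by treatment", with no qualifier about baseline. Its shell, Template T_LB3, has columns for test, treatment, m, H, L and Overall, and no time column. The counting rule is "Subjects only counted once per treatment per category", with Overall counted once per treatment. The denominator is defined as "m = total number of results for that parameter". The programming note says "Continued with all tests, treatment groups and time points".

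The two other pooled out-of-range tables are restricted:

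- Vital signs (T_VS3, Table 14.3.6.3): section 19.1 titles it "Summary of vital signs outside the normal range by treatment and parameter (excluding baseline time point"), and the shell note adds "Only include post-treatment time points".
- ECG (T_EG4, Table 14.3.7.3): the shell title reads "outside the normal range by treatment and category (excluding baseline time point"), and its note carries the same post-treatment restriction. The section 19.1 title for this table lacks the qualifier, but the shell has it.

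Protocol section 12.1, note 18, sets the laboratory schedule: "Samples are to be taken at screening, Day -1, before dosing on Days 8 and 14, on Day 20, and at follow-up". PET subjects have one further chemistry sample at imaging session 1, before the first dose.

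**The concern.** A table pooled over visits and headed by dose group will be read as a count of subjects with abnormal laboratory values while on, or after, that dose. If pre-dose results are included, a subject with a high value on Day -1 and normal values at every later visit is counted as High under an ASN51 dose. Nothing in the table separates that subject from one whose value rose after dosing.

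Eligible subjects can be flagged before dosing. Protocol exclusion 21 bars ALT or AST only from 1.5 times the upper limit of normal, so a smaller elevation is not barred by that criterion. T_LB3 also uses the reference ranges, not the normal ranges used to judge clinical significance. In SAP Appendix A, sodium of 143-145 mmol/L lies within the normal range (137-145) but above the reference range (134-142).

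Laboratory safety is a named secondary endpoint, there is no placebo group, and each dose group has at most 6 subjects, so one wrongly placed subject is 1 in 6. The laboratory counts would also be on a different basis from the vital-sign and ECG counts reported beside them.

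**Working it through.** **1. Does other SAP text supply the missing limit?**

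- Section 14.5 says that data outside the reference ranges are summarised, without a post-baseline limit.
- Section 12.1 keeps unscheduled results out of summaries, but screening, imaging session 1 and Day -1 are scheduled.
- Section 12.2 defines baseline as the last value before study drug. It does not remove baseline from T_LB3.

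None supplies it. The same sentence about time points also stands in T_LB1, where it does no harm because T_LB1 has a row for each planned time.

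**2. Reproduce the plan's sample counts.** Note 18 gives screening, Day -1, Day 8, Day 14, Day 20 and follow-up, which is 6. Imaging session 1 makes chemistry 7 in PET subjects. Protocol Tables 7 and 8 show 6 haematology, 6 coagulation and 6 (PBMC-only) or 7 (PET) chemistry samples. The counts agree.

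**3. Pre-dose share per test in a full group of 6 (4 PET, 2 PBMC-only).**

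| | All scheduled results | Pre-dose | Post-dose | Pre-dose share |
|---|---|---|---|---|
| Haematology or coagulation | 6 × 6 = 36 | 6 × 2 = 12 | 6 × 4 = 24 | 12/36 = 33% |
| Chemistry | 4 × 7 + 2 × 6 = 40 | 4 × 3 + 2 × 2 = 16 | 6 × 4 = 24 | 16/40 = 40% |

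If Day -1 were the only pre-dose visit included, the share would be 6/30 = 20%. These shares follow from the schedule alone.

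**4. Illustration: flagged subjects who are abnormal only before dosing.** The documents give no out-of-range rate and no within-subject correlation, so both are assumed.

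*Correlated results.* Assume no drug effect, normally distributed values, ranges covering 95% of values, and within-subject correlation ρ of 0.5 to 0.8. Given a subject effect u ~ N(0, ρ), one result is in range with probability

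p(u) = Φ((1.96 − u)/√(1 − ρ)) − Φ((−1.96 − u)/√(1 − ρ)).

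The chance of at least one flag in k results is P(k) = 1 − E[p(u)^k], found by numerical integration. The share of flagged subjects with no post-dose flag is 1 − P(4)/P(k).

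| ρ | P(4), post-dose only | P(5), plus Day -1 | P(6), plus Day -1 and screening | Pre-dose only, k = 6 | Pre-dose only, k = 5 |
|---|---|---|---|---|---|
| 0.5 | 0.156 | 0.183 | 0.207 | 1 − 0.156/0.207 = 25% | 1 − 0.156/0.183 = 15% |
| 0.8 | 0.114 | 0.127 | 0.139 | 1 − 0.114/0.139 = 18% | 1 − 0.114/0.127 = 10% |

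*Independent results.* With an out-of-range rate q per result, P(k) = 1 − (1 − q)^k. For q = 1%, 1 − 0.0394/0.0585 = 33%. For q = 10%, 1 − 0.3439/0.4686 = 27%.

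The direction is the same in each case; the size depends on the assumption.

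**The case against.** Several points on the other side stand, and they limit what can be claimed.

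- **Not the only count by dose.** T_LB1 gives High and Low counts by test, treatment and planned time, with pre-dose rows separate. T_LB3 is only the one laboratory table that counts subjects once across visits.
- **Traceable.** Listings 16.2.8.1-16.2.8.3, the stated source of the table, show results by subject, test and planned time, and the example in the shell sets a Day -1 row beside a later one. T_LB2 adds change from baseline. With at most 6 subjects per group, a reader can find every pre-dose-only flag.
- **No causal claim.** A reader might infer that the plan attributes pre-dose abnormalities to ASN51. The documents do not support that: the table is by treatment group and says nothing of emergence or cause. Both dose groups follow the same laboratory schedule, so the comparison between doses is not tilted by design.
- **Intent is not shown.** A reader might infer that the authors meant this table to be post-dose and slipped, or that they chose to include pre-dose results. Neither is established. T_EG4 has almost the same phrase about time points next to its restriction, and T_LB3 agrees with section 14.5. What is established is that the qualifier is absent here and present in the two parallel tables.
- **The illustration may be too high.** Under SAP section 12.2 an out-of-range baseline that is repeated before dosing is replaced by the latest repeat, while later out-of-range values are kept. Exclusions 1 and 21 remove some abnormal values before dosing. The reference ranges are those most commonly used in the study, with no stated 95% coverage.

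The file note that changed some time points (SAP sections 6 and 17) is not among the documents, so the counts follow the protocol schedule.

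None of this supplies the missing restriction. Tracing cases through the listings also does not correct the printed count.

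**Conclusion.** The point holds as a minor but real error in a descriptive safety table. As written, T_LB3 mixes pre-dose and post-dose results in one count per subject under each dose. In a full group, 33% of the scheduled results behind each haematology or coagulation test and 40% behind each chemistry test are pre-dose; these figures assume only that all 6 subjects are enrolled and sampled as scheduled.

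The proportion of flags that are pre-dose only cannot be had from the documents. A value of 18-25% rests on 95% ranges, normality and a within-subject correlation of 0.5-0.8. It falls to 10-15% if only Day -1 is included, and lower if baseline repeats replace out-of-range values. A reader might carry this on to a number of false entries across all tests and subjects; the documents do not support such a figure as an expected error.

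No primary endpoint depends on the table. The dose-escalation review in protocol section 8.5 looks at laboratory safety tests but is not tied to this display.

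**What to change.** In Template T_LB3 and in the section 19.1 title of Table 14.3.4.2, add the parenthesis excluding the baseline time point, as in T_VS3 and the T_EG4 shell. Add to the programming note "Only include post-treatment time points", and remove the reference to all time points.

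Name the excluded visits: screening, imaging session 1 and Day -1. Excluding baseline alone would normally remove only Day -1. State also that the samples taken before dosing on Days 8 and 14 stay in, since they follow the first dose and a filter on a pre-dose label would drop them.

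Compute m on the same results: for a full group it falls from 36 to 24 for each haematology or coagulation test, and from 40 to 24 for each chemistry test. Keep the pre-dose rows in T_LB1.

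The cost is a short shell edit and a filter in the program. No visit, sample or data item changes. The reported counts can only stay the same or become smaller.
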